23. Female has a positive pregnancy test at the Screening or Baseline Visit, is planning to become pregnant, or is breastfeeding.
24. Has ongoing litigation for workers' compensation.
25. Known diagnosis of long QT syndrome.
26. Male has a QRS interval ≥ 120 ms *and* QTcF ≥ 460 ms OR female has a QRS interval ≥ 120 ms *and* QTcF ≥ 480 ms at Screening.
27. Has moderate to severe congestive heart failure (New York Heart Association [NYHA] class III and class IV).
28. Has a history of symptomatic cardiovascular disease.
29. Current therapy with any immunosuppressive therapy, including corticosteroids (>5 mg/day of prednisone).

30. Moderate to severe hepatic impairment at the Screening Visit, as defined by any of the following:

- AST **and** ALT values that are ≥ 1.5 times ULN

31. Moderate to severe renal impairment at the Screening Visit, as defined by either:

- An estimated glomerular filtration rate [eGFR] < 45 mL/min; or
- A serum creatinine level > 1.3 mg/dL.

32. Use of CYP3A4 inhibitors (e.g., grapefruit juice, pantoprazole) or CYP3A4 inducers (e.g., omeprazole, carbamazepine, rifampin, St. John's wort) within 7 days prior to the Baseline Visit. Please see Appendix III. Concomitant Medications.

33. Use of CYP2C9 inhibitors (e.g., amiodarone, fluconazole) or CYP2C9 inducers (e.g. carbamazepine, rifampin, St. John's wort) within 7 days prior to the Baseline Visit. Please see Appendix III. Concomitant Medications.

34. Use of P-glycoprotein inhibitors (e.g., atorvastatin, azithromycin, carvedilol) within 7 days prior to the Baseline Visit or any time during study participation, unless taken for at least 3 months prior and at a stable dose for at least 1 month prior to the Baseline Visit. Please see Appendix III. Concomitant Medications.

35. Is classified as a poor metabolizer via the CYP2C9 pathway as determined by genetic testing (CYP2C9 genotyping).

36. Has clinically significant pulmonary disease such that chronic, daily use of medical treatment is required (e.g. COPD, asthma).

37. Has any of the following blood counts:

- Monocyte count < 1 % of white blood cells (e.g., for WBC = 4,500/ μ L, exclude patient if monocyte count $< 0.01 * 4,500$ or 45/ μ L; for WBC = 11,000/ μ L, exclude patient if monocyte count $< 0.01 * 11,000$ or 110/ μ L)
- Platelet count, or
 - Females (sex at birth): $< 125,000/\mu$ L
 - Males (sex at birth): $< 150,000/\mu$ L
- Hemoglobin:
 - Females (sex at birth): < 11.5 grams/dL
 - Males (sex at birth): < 13.0 grams/dL

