E.5. Rationale for the Inclusion/Exclusion Criteria

The main rationale for inclusion and exclusion criteria is to enroll Subjects who are generally in good health, with chronic pain related to stable clinical course of osteoarthritis of the index knee, and who will be able to participate in this study for the duration of 24 weeks. Subjects that show with renal or hepatic impairment or are poor CYP2C9 metabolizers are excluded for safety reasons. Subjects in this study must be able and willing to provide multiple assessments about their pain and function at home via smartphone using the New England Survey Systems (NESS) app and via tablet at the time of in-person clinic visits. Individuals without a smartphone can be lent one from NESS.

■ STUDY ASSESSMENTS – PLAN AND METHODS

F.1. Study Conduct

Table 1: Schedule of Events

Study Phase	Screening Period		Baseline (Day 0)	Clinic Visits scheduled every 3 weeks (+/- 4 days)																	
	(14-28 days before Baseline)			Wk 0	Wk 0-3	Wk 3	Wk 3-6	Wk 6	Wk 6-9	Wk 9	Wk 9-12	Wk 12	Wk 12-15	Wk 15	Wk 15-18	Wk 18	Wk 18-21	Wk 21	Wk 21-24	Wk 24 Final Visit/ET ¹	
Study Week	Screen Visit	Screen Period	V1		V2		V3		V4		V5		V6		V7		V8		V9		
Clinic (C) Visit or Mobile (M) Visit	C	M	C	M	C	M	C	M	C	M	C	M	C	M	C	M	C	M	C	C	
Informed Consent	X																				
Review Eligibility Criteria	X	X	X																		
Randomization			X																		
IXRS Drug Dispensing			X		X		X		X		X		X		X		X		X		
ASSESSMENTS																					
Radiograph Imaging – Chest ²	X																				X
Radiograph Imaging – Both Knees ³	X																				
K-L Grade Confirmation by Central Radiologist ³	X																				
12 – lead ECG	X		X		X		X		X		X		X		X		X		X		X
CYP2C9 Genotyping	X																				

Study Visit	Screening	V1		V2		V3		V4		V5		V6		V7		V8		V9
Physical Examination	X																	X
Vital Signs	X		X			X				X				X				X
Height and Weight BMI	X																	X
Contraceptive Use	X																	
Adverse Events	X		X		X		X		X		X		X		X		X	X
Medical History, OA History	X																	
Demographics	X																	
Analgesic Rescue Medication Use ⁴	X	X	X	X	X	X	X	X	X	X	X	X	X	X	X	X	X	X
Concomitant Medications and Therapies ⁵	X		X		X		X		X		X		X		X		X	X
SAFER Interview ⁶		X																
Drug Accountability and Compliance			X		X		X		X		X		X		X		X	X
PROTOCOL PATIENT MEASURES – NEForm (NESS)																		
Distribute Smart Device (if applicable)	X																	

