F.3.1.1. Automatic Stopping Criteria for Subjects

If a subject meets any of the following criteria at any time during the study, they must be discontinued from the study drug and withdrawn from participation, in accordance with the procedures outlined in Section F.3.2.

- a. 1) ALT and/or AST $>3x$ ULN with total bilirubin $>2x$ ULN (unless elevated bilirubin is related to confirmed Gilbert's Syndrome). Subjects with total serum bilirubin $>2x$ above ULN will be followed until resolution. 2) Confirmed AST and/or ALT $>5x$ ULN for more than 2 weeks.
- b. Serum creatinine $>1.5 \times$ ULN or Grade 2 (moderate) value based on Toxicity Grading Scale for Healthy Adult and Adolescent Volunteers Enrolled in Preventive Vaccine Clinical Trials.

- c. ECGs (minimum criteria): absolute QTcF \geq 500 ms; absolute QTcF $<$ 320 ms (clinically significant QTc shortening); prolongation in repeated, averaged ECG measures of PR or QRS of $>$ 40 ms from the Baseline Visit.
- d. Monocyte count $<$ 1% of white blood cells (e.g., for WBC = 4,500/ μ L, stop if monocyte count $<$ 0.01 * 4,500 or 45/ μ L), hemoglobin $<$ 11 g/dL (Grade 2 in females) or $<$ 12.4 g/dL (Grade 2 in males), platelets $<$ 100,000/ μ L on 2 consecutive blood draws. A confirmatory blood draw will be completed at an in-clinic unscheduled visit. Discontinuation will be confirmed by the consecutive blood draw at the next in-clinic visit.

F.3.2. Discontinuation of Subjects who Stopped taking Study Medication

Should a patient discontinue study medication and decide to withdraw consent, an EOS visit should be scheduled at the earliest convenience to complete the EOS study procedures, unless the subject agrees to schedule it for the next study visit.

Should a patient discontinue study medication, but not withdraw consent, best efforts should be made by the site to collect all study data at the regular study assessment times through the closest of the following study visits: Week 6, Week 12, Week 18 or Week 24/ET. At this clinic visit, all assessments outlined for the EOS visit should be conducted.

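### Exclusions 26 and 30 admit Screening ECG and liver values that already meet an automatic stopping rule

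*Protocol*

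**What the plan says.** **Entry (Protocol E.4.2).** Exclusion 26 applies to a man when "Male has a QRS interval ≥ 120 ms *and* QTcF ≥ 460 ms"; for a woman the QTcF limit is 480 ms with the same QRS condition. It has no lower QTcF limit. Exclusion 25 covers only a known diagnosis of long QT syndrome, not a measured value. Exclusion 30 defines moderate to severe hepatic impairment by a single bullet, "AST and ALT values that are ≥ 1.5 times ULN", with no bilirubin limit. The stated purpose, in E.5, is that "Subjects that show with renal or hepatic impairment or are poor CYP2C9 metabolizers are excluded for safety reasons"; F.2.7 repeats the intention for moderate to severe impairment.

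**Stopping (Protocol F.3.1.1).** For subjects who meet a listed criterion, "they must be discontinued from the study drug and withdrawn from participation, in accordance with the procedures outlined in Section F.3.2". Criterion (a)(1) is "ALT and/or AST $>3x$ ULN with total bilirubin $>2x$ ULN", unless the bilirubin is explained by confirmed Gilbert's syndrome. Criterion (a)(2) is "Confirmed AST and/or ALT $>5x$ ULN for more than 2 weeks". Criterion (c) begins "ECGs (minimum criteria): absolute QTcF" and sets a limit of 500 ms or more. Its lower limit is a value below "320 ms (clinically significant QTc shortening". Neither absolute QTcF limit has a QRS condition.

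**The concern.** For the same measurement, an entry rule should not be looser than the rule that takes a patient off the drug. Here the entry rules join their components with *and*, while the stops act on QTcF alone or on either transaminase together with bilirubin. A patient could pass the numeric criteria and take a first dose at a value where the protocol says dosing must cease.

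Both measurements matter for this compound. Protocol A.1 reports QTc prolongation in monkeys at 250 mg/kg (not at 50 mg/kg) and raised transaminases in the high-dose monkey group. Earlier human exposure to 300 mg BID lasted 10 days, whereas each treatment period here lasts 6 weeks. Against that, the Phase 1 studies showed no clinically meaningful ECG or laboratory changes.

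**Working it through.** No power or sample-size figure is involved. The check treats exclusions 26 and 30 and stops (a)(1) and (c) as logical rules and applies both to the same Screening values.

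**Rules**

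- Exclusion 26: QRS >= 120 ms AND QTcF >= 460 ms (men) or >= 480 ms (women).
- Stop (c), absolute part: QTcF >= 500 ms OR QTcF < 320 ms. The PR and QRS parts of (c) are changes from Baseline, so they cannot be met at Screening.
- Exclusion 30: AST >= 1.5x ULN AND ALT >= 1.5x ULN.
- Stop (a)(1): (AST > 3x ULN OR ALT > 3x ULN) AND total bilirubin > 2x ULN, without confirmed Gilbert's syndrome.

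**ECG cases**

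| Sex | QRS (ms) | QTcF (ms) | Excluded by 26? | Meets stop (c)? |
|---|---|---|---|---|
| M or F | 100 | 505 | no | yes |
| M or F | 119 | 500 | no | yes |
| M or F | 120 | 500 | yes | yes |
| M | 100 | 315 | no | yes |
| F | 130 | 315 | no | yes |

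With QTcF of 500 ms or more, the gap covers every QRS below 120 ms. With QTcF below 320 ms it covers every QRS, because such a value can never reach 460 or 480 ms.

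**Liver cases (multiples of ULN, no Gilbert's syndrome)**

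| AST | ALT | Bilirubin | Excluded by 30? | Meets stop (a)(1)? |
|---|---|---|---|---|
| 1.2 | 4 | 2.5 | no | yes |
| 3.5 | 1.4 | 2.5 | no | yes |
| 1.49 | 3.01 | 2.01 | no | yes |
| 1.5 | 4 | 2.5 | yes | yes |
| 1.4 | 6 | 1.0 | no | no |

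The liver gap is exactly this: one enzyme above 3x, the other below 1.5x, and bilirubin above 2x ULN. The last row is not counted, because stop (a)(2) needs a confirmed elevation lasting more than 2 weeks and one Screening value cannot meet it.

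**Comparison with haematology (exclusion 37 against stop (d), entry limit minus stop limit)**

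- Haemoglobin, women: 11.5 - 11 = 0.5 g/dL; men: 13.0 - 12.4 = 0.6 g/dL.
- Platelets, women: 125,000 - 100,000 = 25,000/uL; men: 150,000 - 100,000 = 50,000/uL.
- Monocytes: 1% - 1% = 0.

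All three haematology entry limits are at, or stricter than, their stops. The ECG and liver rules do not follow that pattern.

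**Creatinine.** The 1.3 mg/dL limit in exclusion 31 is looser than a stop at 1.5x ULN only if the local ULN is below 1.3 / 1.5 = 0.87 mg/dL. The documents give no ULN. The other limb of stop (b) refers to an external toxicity scale that they do not reproduce. No claim is made about creatinine.

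**The case against.** Eligibility depends on all the criteria, not two of them. Exclusion 19 bars laboratory results the investigator considers clinically significant, and exclusion 16 bars conditions that might affect safety. An investigator must review every ECG report for safety concerns or reasons to exclude (F.2.1), and out-of-range laboratory results are graded for clinical significance. Table 1 note 12 contemplates screen failure after a repeat test. The SAFER team checks the other screening criteria before scheduling its interview (F.1.3), the Medical Monitor and protocol PI review abnormal laboratory values (F.2.7), and criteria are confirmed again before randomisation (F.1.5). Exclusions 25 and 28 remove some cardiac cases. F.3.1.1 applies throughout the study, and F.2.4 uses discontinuation language for a SAFER screen failure, so a site might read the stops as covering screened patients. ECG and chemistry are repeated at Baseline, so a persisting abnormality would be seen again. The examples are constructed and no analysis result changes.

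Much of this stands: enrolment of such a patient is unlikely. It does not close the gap. Exclusions 16 and 19 and the ECG and laboratory reviews rest on judgement and supply no number. The SAFER and pre-randomisation checks apply the written criteria, which are the incomplete ones. F.3.1.1 works by stopping study drug and points to F.3.2, which is for subjects who have stopped medication; it does not define eligibility. The protocol leaves no discretion at these values once dosing has begun, so leaving them to discretion before the first dose is inconsistent.

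**Conclusion.** The concern holds. Two automatic stops, (a)(1) and the absolute QTcF part of (c) with its two limits, can be met at Screening by a patient who passes exclusions 26 and 30. None of the three haematology stops can be met by a patient who passes exclusion 37.

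The conclusion rests on the current wording of E.4.2 and F.3.1.1 and, for the liver case, on the absence of confirmed Gilbert's syndrome. The number of patients cannot be derived and is probably small. This is a safety and consistency correction that should be made; it does not affect sample size, power or the efficacy analysis.

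**What to change.** Add one exclusion to E.4.2: a patient may not be randomised if the Screening ECG or chemistry, after any permitted repeat, shows QTcF of 500 ms or more, QTcF below 320 ms, or ALT and/or AST above 3x ULN with total bilirubin above 2x ULN (unless Gilbert's syndrome is confirmed).

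Add one sentence to F.3.1.1: criterion (a)(1) and the absolute QTcF limits in (c) also apply to Baseline results, with drug withheld or stopped as soon as such a result is known. For a subject already dosed this largely restates the existing rule, but it removes doubt. First dosing should not wait for the central ECG reading or the laboratory report.

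Changing *and* to *or* in exclusions 26 and 30 would not be enough: QTcF below 320 ms with QRS below 120 ms would still pass. That wording, the 460/480 ms and 1.5x ULN limits, and any single-test limit at 5x ULN are for the sponsor's clinicians.

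The cost is two sentences and possibly a few more screen failures. All the tests are already scheduled, and nothing is added to the Baseline visit, where the first dose is normally taken.

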3. NIH HEAL CDE
 - a) PGIC
4. Blood Collection – Lab Chemistry
5. Urine Collection – urine dipstick
 - a) If abnormal for leukocytes, blood, nitrite, or protein, complete full urinalysis.
6. Other Assessments
 - a) Document concomitant medications (using generic names).
 - b) Review of analgesic rescue medication with the patient
 - c) ECG (12-Lead)
 - d) Record adverse events
 - e) Drug Accountability and Compliance
7. Use Almac's IXRS to get the next kit assignment.
 - a) Dispensation of study drug (1 kit; 2 bottles)

Remote procedures to be completed between V2/Week 3 & V3/Week 6:

8. Remote Protocol Patient Measures – PROs – Use NEForm App
 - a) WOMAC-A – completed once weekly
 - b) End of Day Pain Ratings – NRS (0-10) - completed once daily for the week prior to the next visit
9. Other Remote Assessments – completed once daily
 - a) Concomitant rescue medication – captures use of acetaminophen and opioids daily
 - b) Study Medication – captures time and confirms dosing twice daily
 - i. Failure to document 6 consecutive doses (3 days) of study medication is grounds for early termination. Monitor for missed doses and reeducate patient as needed.

F.1.8. Visit 3 (Week 6)

For all visits, NEForm will be used to record the PRO scales. All other data will be directly entered into the study database or collected externally and entered into the EDC with source materials uploaded to Florence. Additional information and instructions on study activities can be found in the MOP.

1. Review remote forms completion rate with patient
2. Protocol Patient Measures
 - a) PROs
 - i. WOMAC-A (Pain Scale)
Must obtain WOMAC-A before synovial fluid collection procedure
 - ii. WOMAC-C (Functional Scale).
 - iii. HADS
 - b) Staircase-Evoked Pain Assessment.
3. Lab Draws/Collections
 - a) Blood Draws:
 - i. Chemistry
 - ii. Hematology
 - iii. PK Analysis (see section F.2.2)
 - iv. Biomarker - Cytokines & Chemokines (see section F.2.2)
 - b) Urine dipstick
 - i. If abnormal for leukocytes, blood, nitrite, or protein, complete full urinalysis.
 - c) Synovial Fluid (Knee) Collection
 - i. **If subject opted out of synovial fluid DO NOT collect**
 - ii. Collect and ship to Myriad Lab for analysis
 - d) Biobanking (See Section F.2.3; See MOP, Laboratory Manual)
 - i. **If a subject has opted out of biobanking DO NOT collect**
 - ii. Collect and freeze leftover blood and synovial fluid samples to batch ship to NYU's biorepository
4. NIH HEAL Initiative CDEs for chronic pain (Use NEForm)
 - a) PROMIS Sleep Disturbance Scale – 6A.
5. Other Assessments
 - a) Document concomitant medications (using generic names).
 - b) Review of analgesic rescue medication
 - c) Vital signs, as detailed in Section F.2.1
 - d) ECG (12-Lead)
 - e) Drug accountability and compliance.
 - f) Record adverse events.
6. Use Almac's IXRS to get the next kit assignment.
 - a) Dispensation of study drug (1 kit; 2 bottles)

Remote procedures to be completed between V3/Week 6 & V4/Week 9:

7. Remote Protocol Patient Measures
 - a) WOMAC-A (Pain Scale) – completed once weekly
 - b) End of Day Pain Ratings – NRS (0-10) – completed once daily for the seven days prior to the next visit
8. Other Remote Assessments – completed once daily
 - a) Concomitant rescue medication – captures use of acetaminophen and opioids daily
 - b) Study Medication – captures time and confirms dosing twice daily
 - i. Failure to document 6 consecutive doses (3 days) of study medication is grounds for early termination. Monitor for missed doses and reeducate patient as needed.

F.1.9. Visit 4 (Week 9)

For all visits, NEForm will be used to record the PRO scales. All other data will be directly entered into the study database or collected externally and entered into the EDC with source materials uploaded to Florence. Additional information and instructions on study activities can be found in the MOP.

1. Review remote forms completion rate with patient
2. Protocol Patient Measures - PROs
 - a) WOMAC-A (Pain Scale).
 - b) WOMAC-C (Functional Scale)
3. Blood Collection – Lab Chemistry
4. Urine Collection – Urine Dipstick
 - a) If abnormal for leukocytes, blood, nitrite, or protein, complete full urinalysis
5. Other Assessments
 - a) Review concomitant medications (using generic names)
 - b) Review of analgesic rescue medication
 - c) ECG (12-Lead)
 - d) Record adverse events
 - e) Drug Accountability and Compliance
6. Use Almac's IXRS to get the next kit assignment.
 - a) Dispensation of study drug (1 kit; 2 bottles)

Remote procedures to be completed between V4/Week 9 & V5/Week 12:

7. Remote Protocol Patient Measures
 - a) WOMAC-A (Pain Scale) – completed once weekly
 - b) End of Day Pain Ratings – NRS (0-10) - completed once daily for the seven days prior to the next visit

8. Other Remote Assessments – completed once daily
 - a) Concomitant rescue medication – captures use of acetaminophen and opioids daily
 - b) Study Medication – captures time and confirms dosing twice daily
 - i. Failure to document 6 consecutive doses (3 days) of study medication is grounds for early termination. Monitor for missed doses and reeducate patient as needed.

F.1.10. Visit 5 (Week 12)

For all visits, NEForm will be used to record the PRO scales. All other data will be directly entered into the study database or collected externally and entered into the EDC with source materials uploaded to Florence. Additional information and instructions on study activities can be found in the MOP.

1. Review remote forms completion rate with patient
2. Protocol Patient Measures
 - a) PROs
 - i. WOMAC-A (Pain Scale).
 - ii. WOMAC-C (Functional Scale).
 - iii. HADS
 - b) Staircase-Evoked Pain Assessment.
3. NIH HEAL Initiative CDEs for chronic pain
 - a) PROMIS Sleep Disturbance Scale – 6A.
4. Lab Draws/Collection
 - a) Blood Draws:
 - i. Chemistry
 - ii. Hematology
 - iii. Biomarkers - Cytokines & Chemokines (See Section F.2.2)
 - iv. PK Analysis (See Section F.2.2)
 - b) Biobanking (See Section F.2.3; See MOP, Laboratory Manual)
 - i. **If a subject has opted out of biobanking DO NOT collect**
 - ii. Send leftover blood samples to NYU biorepository for future testing
 - c) Urine dipstick analysis
 - i. If abnormal for leukocytes, blood, nitrite, or protein, complete full urinalysis.
 - d) Urine pregnancy test (kit provided by study) for WOCBP
 - i. If positive, a serum pregnancy test should be performed.
5. Other Assessments
 - a) Document concomitant medications (using generic names).
 - b) Vital signs, as detailed in Section F.2.1
 - a) Review of analgesic rescue medication with patient using data from NEForm.
 - c) ECG (12-lead).
 - d) Drug Accountability and Compliance.

- e) Record adverse events.
- f) Placebo Response Mitigation Training, as a part of the NEForm (NESS) electronic assessments, patients will be presented with a placebo response mitigation transcript at the Screening and Week 12 visits. These instructions recommend patients answer questions while sitting alone in a quiet area free of distraction. The instruction also advises patients to focus only on pain in the index knee, ignoring pain in other areas and sensations in the index knee that are not painful (e.g. stiffness).

6. Use Almac's IXRS to get the next kit assignment

- a) Dispensation of study drug (1 kit; 2 bottles)

Remote procedures to be completed between V5/Week 12 & V6/Week 15:

- 7. Remote Protocol Patient Measures
 - a) WOMAC-A (Pain Scale) – completed once weekly
 - b) End of Day Pain Ratings – NRS (0-10) -completed once daily for the seven days prior to the next visit
- 8. Other Remote Assessments – completed once daily
 - a) Concomitant rescue medication – captures use of acetaminophen and opioids daily
 - b) Study Medication – captures time and confirms dosing twice daily
 - i. Failure to document 6 consecutive doses (3 days) of study medication is grounds for early termination. Monitor for missed doses and reeducate patient as needed.

F.1.11. Visit 6 (Week 15)

For all visits, NEForm will be used to record the PRO scales. All other data will be directly entered into the study database or collected externally and entered into the EDC with source materials uploaded to Florence. Additional information and instructions on study activities can be found in the MOP.

1. Review remote forms completion rate with patient
2. Protocol Patient Measures -PROs
 - a) WOMAC -A (Pain Scale)
 - b) WOMAC-C (Functional Scale)
3. Lab Draws/Collections:
 - a) Blood Draw – Lab Chemistry
 - b) Urine dipstick Urine dipstick analysis
 - i. If abnormal for leukocytes, blood, nitrite, or protein, complete full urinalysis.
4. Other Assessments
 - a) Document concomitant medications (using generic names).
 - b) Review of analgesic rescue medication with patient using data from NEForm.
 - c) Record adverse events
 - d) ECG (12-Lead)

- e) Drug Accountability and Compliance
- 5. Use Almac's IXRS to get the next kit assignment
 - a) Dispensation of study drug (1 kit; 2 bottles)

Remote procedures to be completed between V6/Week 15 & V7/Week 18:

- 6. Remote Protocol Patient Measures
 - a) WOMAC-A (Pain Scale) – completed once weekly
 - b) End of Day Pain Ratings – NRS (0-10) - completed once daily for the seven days prior to the next visit
- 7. Other Remote Assessments – completed once daily
 - a) Concomitant rescue medication – captures use of acetaminophen and opioids daily
 - b) Study Medication – captures time and confirms dosing twice daily
 - i. Failure to document 6 consecutive doses (3 days) of study medication is grounds for early termination. Monitor for missed doses and reeducate patient as needed.

F.1.12. Visit 7 (Week 18)

For all visits, NEForm will be used to record the PRO scales. All other data will be directly entered into the study database or collected externally and entered into the EDC with source materials uploaded to Florence. Additional information and instructions on study activities can be found in the MOP.

- 1. Review forms completion rate with patient
- 2. Protocol Patient Measures
 - a) PROs
 - i. WOMAC-A (Pain Scale).
 - ii. WOMAC-C (Functional Scale).
 - iii. HADS
 - b) Staircase-Evoked Pain Assessment.
- 3. NIH HEAL Initiative CDEs for chronic pain
 - a) PROMIS Sleep Disturbance Scale – 6A.
- 4. Lab Draws/Collection
 - a) Blood Draws:
 - i. Chemistry
 - ii. Hematology
 - iii. Biomarkers – Cytokines & Chemokines (see section F.2.2)
 - iv. PK Analysis (see section F.2.2)
 - b) Biobanking (See Section F.2.3; See MOP, Laboratory Manual)

- i. If a subject has opted out of biobanking **DO NOT** collect
- ii. Send leftover blood samples to NYU biorepository for future testing
- c) Urine dipstick
 - i. If abnormal for leukocytes, blood, nitrite, or protein, complete full urinalysis.

5. Other Assessments

- a) Document concomitant medications (using generic names).
- b) Vital signs, as detailed in Section F.2.1.
- c) ECG (12-Lead)
- d) Review of analgesic rescue medication use
- e) Drug Accountability and Compliance
- f) Record adverse events.

6. Use Almac's IXRS to get the next kit assignment

- a) Dispensation of study drug (1 kit; 2 bottles) for Weeks 18-21

Remote procedures to be completed between V7/Week 18 & V8/Week 21:

7. Remote Protocol Patient Measures

- a) WOMAC-A (Pain Scale) – completed once weekly
- b) End of Day Pain Ratings – NRS (0-10) - completed once daily for the seven days prior to the next visit

8. Other Remote Assessments – completed once daily

- a) Concomitant rescue medication – captures use of acetaminophen and opioids daily
- b) Study Medication – captures time and confirms dosing twice daily
 - i. Failure to document 6 consecutive doses (3 days) of study medication is grounds for early termination. Monitor for missed doses and reeducate patient as needed.

F.1.13. Visit 8 (Week 21)

For all visits, NEForm will be used to record the PRO scales. All other data will be directly entered into the study database or collected externally and entered into the EDC with source materials uploaded to Florence. Additional information and instructions on study activities can be found in the MOP.

1. Review forms completion rate with patient
2. Protocol Patient Measures -PROs
 - a) WOMAC-A (Pain Scale)
 - b) WOMAC-C (Functional Scale)
3. Blood Collection – Lab Chemistry
4. Urine dipstick

- a) If abnormal for leukocytes, blood, nitrite, or protein, complete full urinalysis.

5. Other Assessments

- a) Document concomitant medications (using generic names).
- b) Review of analgesic rescue medication with patient using data from NEForm.
- c) ECG (12-Lead)
- d) Record adverse events
- e) Drug Accountability and Compliance

Remote procedures to be completed between V8/Week 21 & V9/Week 24

6. Remote Protocol Patient Measures –

- a) WOMAC-A (Pain Scale) – completed once weekly
- b) End of Day Pain Ratings – NRS (0-10) -completed once daily for the seven days prior to the next visit

7. Other Remote Assessments – completed once daily

- a) Concomitant rescue medication – captures use of acetaminophen and opioids daily
- b) Study Medication – captures time and confirms dosing twice daily
 - i. Failure to document 6 consecutive doses (3 days) of study medication is grounds for early termination. Monitor for missed doses and reeducate patient as needed.

F.1.14. Visit 9 (Week 24 or Early Termination)

For all visits, NEForm will be used to record the PRO scales. All other data will be directly entered into the study database or collected externally and entered into the EDC with source materials uploaded to Florence. Additional information and instructions on study activities, can be found in the MOP.

1. Review forms completion rate with patient
2. Protocol Patient Measures – NEForm on Tablet
 - a) PROs
 - i. WOMAC-A (Pain Scale)
 - ii. WOMAC-C (Functional Scale)
 - iii. HADS
 - b) Staircase-Evoked Pain Assessment
3. NIH HEAL Initiative CDEs for chronic pain – NEForm on Tablet
 - a) PEG Scale.
 - b) Pain Catastrophizing Scale – Short Form 6.
 - c) PROMIS Sleep Disturbance Scale – 6A.
 - d) Sleep Duration Question
 - e) PROMIS Physical Functioning Short-Form 6b.
 - f) PHQ – Depression.

- g) GAD-2
- h) PGIC
- i) TAPS-1
- j) OUQ

4. Lab Draws/Collection

- a) Blood Draws:
 - i. Chemistry
 - ii. Hematology
 - iii. Biomarkers – Cytokines & Chemokines (See Section F.2.2)
 - iv. PK Analysis (See Section F.2.2)
- b) Urine Dipstick
 - i. If abnormal for leukocytes, blood, nitrite, or protein, complete full urinalysis.
- c) Urine Drug Screen – test kit provided by study
- d) Urine Pregnancy Test for WOCBP – if positive confirm with serum pregnancy test
- e) Biobanking (See Section F.2.3; See MOP, Laboratory Manual)
 - i. **If a subject has opted out of biobanking DO NOT collect**
 - ii. 10ml of whole blood will be collected and frozen to batch ship to NYU's biorepository
 - iii. Freeze leftover blood samples to batch ship to NYU's biorepository

5. Other Assessments

- a) Physical examination.
 - i. A pelvic or urogenital examination may be deferred unless the investigator deems this to be clinically indicated.
- b) Document Concomitant medications (using generic names).
- c) Review of analgesic rescue medication use.
- d) Chest Radiograph - posterior-anterior only
- e) ECG (12-Lead)
- f) Vital signs, as detailed in Section F.2.1.
- g) Drug Accountability and Compliance
- h) Record adverse events.

6. If applicable, collect NESS loaner device from subjects.

F.2. Procedures

F.2.1. Laboratory/Diagnostic Procedures

As outlined in Table 1, after the patient has signed the informed consent document, laboratory procedures will be conducted regularly to confirm subject safety. Urine and blood tests may be repeated per PI discretion and Medical Monitor approval before a subject is screen failed (during screening) or discontinued from study participation.

1. Urine Pregnancy Test: A urine pregnancy test will be performed at the Screening Visit, Baseline Visit, Week 12 (Visit 5), and Week 24/ET (Visit 9) using the test kit provided by the study.
 - In the event of a positive urine pregnancy test, a serum pregnancy test will be conducted to confirm.
 - If a urine pregnancy test is positive at the Baseline Visit, hold randomization until the serum pregnancy test can verify the results.
 - Subjects with a positive serum pregnancy test at Screening or Baseline will be excluded from the study. Subjects with positive serum pregnancy test results after Baseline will be discontinued from study participation.
 - Additional serum or urine pregnancy tests may be performed as determined necessary by the Investigator or required by local regulation, to establish the absence of any pregnancy any time during study participation.
2. Urine Drug Screen: A urine drug screen will be conducted at the Screening Visit and Week 24/ET (Visit 9) using the test kit provided by the study. The urine drug screen will include amphetamines, barbiturates, buprenorphine, benzodiazepines, cocaine, ecstasy, methamphetamine, methadone, marijuana, opiates, oxycodone, and phencyclidine.
 - If positive, the subject will have the opportunity to provide evidence of medical necessity for their result, e.g. positive for oxycodone due to prescribed intermittently for their OA pain. The Medical Monitor will make the final decision regarding medical support for any positive results.
 - For this study, continuing intermittent opioid use is allowed as a rescue analgesic medication. See Appendix III and MOP for additional information.
 - For this study, medical marijuana (or equivalent) use is allowed for use depending on regional legality.
3. ECG: 12-lead ECGs will be measured at all in-clinic visits.
 - All ECG tracings should be checked for completeness and potential artifacts during the visit. If poor quality or otherwise indicated, additional ECG assessments can be made at the discretion of the investigator.
 - All ECG tracings will be uploaded to ERT (central ECG laboratory) and read at the scheduled time points by a central reader. The site will download the ECG report results from the ERT portal.
 - An investigator at the site is required to review all ECG reports to assess for potential safety concerns or exclusionary reasons. Any abnormalities noted by the central reader must be assessed by the Investigator for clinical significance (CS/NCS) on the report with a date and signature or initials:
 - Abnormal and Not Clinically Significant (NCS)
 - Abnormal and potentially Clinically Significant (CS)

- Any ECG results that are judged by the Investigator to be potentially CS will be recorded on the ECG report and the eCRF. This would constitute an AE and should be entered on the Adverse Event Form and monitored as described in Section F.4.8.1 Adverse Event Reporting. Repeat or unscheduled samples may be taken for safety reasons or to address technical issues with the samples.
- The site will upload the report with the investigator's signature and assessment to Florence within 3-business days of receipt of the ERT report. If technical issues arise, please refer to the ERT manual for other methods of transmission. See **MOP Appendix AC. Investigator Source Expectations and DDE Expectations** for investigator requirements.

4. **Clinical Blood Lab Tests:** Chemistry will be obtained at each in-clinic visit. Hematology will be obtained at the Screening Visit, and at the Weeks 6, 12, 18, and 24/ET Visits.

- **Chemistry:** Sodium, potassium, chloride, calcium, phosphate, magnesium, glucose, urea nitrogen (BUN/Urea), creatinine, uric acid, bilirubin (total and indirect), alkaline phosphatase, AST, ALT, GGT, eGFR, amylase, lipase, total protein and albumin.
 - Estimated glomerular filtration rate [eGFR] will be calculated in the EDC system using Modification of Diet in Renal Disease (MDRD) Study equation and must be assessed by the Investigator for clinical significance (CS/NCS).
- **Hematology:** White cell count with differential (absolute values of neutrophil, lymphocyte, monocyte, eosinophil, and basophil), red cell count, hemoglobin, hematocrit, mean corpuscular volume (MCV), mean corpuscular hemoglobin (MCH), MCH Concentration (MCHC) and platelets count
 - The actual dates and times of sample collection must be recorded in the subject source notes or the laboratory requisition form. All clinical laboratory test results outside the reference range must be assessed by the Investigator for clinical significance (CS/NCS) on the report with a date and signature or initials: Abnormal and Not Clinically Significant (NCS)
 - Abnormal and potentially Clinically Significant (CS)

Any laboratory test results that are judged by the Investigator to be potentially CS will be recorded on the /lab report and the eCRF. This would constitute an AE and should be entered on the Adverse Event Form and monitored as described in Section F.4.8.1 Adverse Event Reporting. Repeat or unscheduled samples may be taken for safety reasons or to address technical issues with the samples.

The site will upload the lab report with the investigator's signature and assessment to Florence within 3-business days. See **MOP Appendix AC. Investigator Source Expectations and DDE Expectations** for investigator requirements.

5. **Vital Signs:** Oral temperature, pulse, respiratory rate and blood pressure will be recorded at the Screening Visit, Baseline Visit, and at the Weeks 6, 12, 18, and 24/ET Visits.

- Patients should be **seated** for 2 minutes prior to collecting pulse and blood pressure.

6. Physical Exam: At the Screening Visit and Week 24/ET (Visit 9), patients will have a physical examination.
 - Genitourinary evaluations will not be conducted, unless deemed necessary by the investigator.
7. CYP2C9 Genotyping: At the Screening Visit, a buccal swab, saliva, or blood sample will be collected to identify and exclude poor CYP2C9 metabolizers. The results must be reviewed before a subject is randomized.
8. Urine Testing:
 - At Baseline, a full urinalysis panel will be done for all subjects, including color, clarity, specific gravity, pH, leukocyte esterase, protein, glucose, ketones, bilirubin, blood, nitrite, urobilinogen.
 - After Baseline, a Urine Dipstick will be completed at all in-clinic visits and will include Calcium, Glucose, Protein, pH, Bilirubin, Blood, Urobilinogen, Micro albumin, Ascorbate, & Specific Gravity. If the dipstick test is abnormal for leukocyte, blood, nitrite or protein, a sample should be sent for a full urinalysis panel.

The required laboratory tests are listed in Table 2, below. Laboratory tests will be performed at the site, and each site will provide their laboratory certificates and normal ranges to the coordinating center. Reference ranges have been standardized across study sites for lipase and amylase due to institutional variability and are as follows, please refer to protocol *Appendix IV Amylase and Lipase Normal Ranges Memo_12Jan2024* for additional information.

F.2.1.1. Table 2: Frequency of Laboratory & Diagnostic Procedures

Laboratory Test	Frequency
Hematology (local lab) [#]	Screening and Week 6, 12, 18, and 24/ET
Chemistry (local lab) [#]	Screening, Baseline, Weeks 3, 6, 9, 12, 15, 18, 21, and 24/ET
Urine Dip Stick ^	Weeks 3, 6, 9, 12, 15, 18, 21, and 24/ET
Urinalysis (UA) ^	Complete UA panel at Baseline; for abnormalities at Weeks 3, 6, 9, 12, 15, 18, 21, and 24/ET
Pregnancy test (urine) using kit provided *	Screening, Baseline, and Weeks 12 and 24/ET
Drug Screen (urine) using kit provided	Screening and Week 24/ET
CYP2C9 Genotyping	Screening

[#] For a full list of tests conducted, please see Section F.2.1.

[^] Microscopic examination will only be performed if the dipstick test is outside of the reference range for leukocyte, blood, nitrite, or protein.

^{*} Only for WOCBP. If urine pregnancy test is positive, a serum pregnancy test will be conducted.

F.2.2. Blood and Synovial Fluid Biomarkers (Cytokines and Chemokines)

